10.5 Other Required Reporting

10.51 Unanticipated Problems Involving Risks to Subjects or Others (UPIRTSO) in general, include any incident, experience, or outcome that meets **all** of the following criteria:

1. Unexpected (in terms of nature, severity, or frequency) given (a) the research procedures that are described in the protocol-related documents, such as the IRB-approved research protocol and informed consent document; and (b) the characteristics of the subject population being studied;
2. Related or possibly related to participation in the research (in this guidance document, possibly related means there is a reasonable possibility that the incident, experience, or outcome may have been caused by the procedures involved in the research); and
3. Suggests that the research places subjects or others at a greater risk of harm (including physical, psychological, economic, or social harm) than was previously known or recognized.

Some unanticipated problems involve social or economic harm instead of the physical or psychological harm associated with adverse events. In other cases, unanticipated problems place subjects or others at increased *risk* of harm, but no harm occurs.

Note: If there is no language in the protocol indicating that pregnancy is not considered an adverse experience for this trial, and if the consent form does not indicate that subjects should not get pregnant/impregnate others, then any pregnancy in a subject/patient or a male patient's partner (spontaneously reported) which occurs during the study or within 120 days of completing the study should be reported as a UPIRTSO.

If the event meets the criteria for an UPIRTSO, submit to your IRB as required by your institutional policies.

10.52 Baseline and Adverse Events Evaluations

The following pre-treatment symptoms/conditions are to be graded at baseline and adverse events are to be graded at each evaluation using CTCAE v5.0 grading.

System Organ Class (SOC)	Adverse event/Symptoms	Baseline	Each Evaluation
General disorders and administration site conditions	Fatigue	X	X
Gastrointestinal disorders	Diarrhea	X	X
Skin and subcutaneous tissue disorders	Rash acneiform	X	X

10.53 **Case Report Forms** - Academic and Community Cancer Research United (ACCRU)

Submit the following AEs not specified in Section 10.5

10.531 Grade 2 AEs deemed *possibly, probably, or definitely* related to the study treatment or procedure.

10.532 Grade 3 and 4 AEs regardless of attribution to the study treatment or procedure.

10.533 Grade 5 AEs (Deaths)

10.5331 Any death within 30 days of the patient's last study treatment or procedure regardless of attribution to the study treatment or procedure.

10.5332 Any death more than 30 days after the patient's last study treatment or procedure that is felt to be at least possibly treatment related must also be submitted as a Grade 5 AE, with a CTCAE type and attribution assigned.

10.54 Late occurring adverse events are any adverse events that occur during Survival Follow-Up reporting periods. These are reported in compliance with Section 4.0 and Section 18.

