2.2 Secondary

- 2.21 To compare the progression free survival (PFS) in molecularly selected patients with metastatic CRC receiving panitumumab rechallenge versus standard therapy (TAS-102 or regorafenib).
- 2.22 To define the objective response rate (ORR) in patients receiving panitumumab rechallenge versus standard therapy (TAS-102 or regorafenib).
- 2.23 To define the clinical benefit rate (CBR= complete response + partial response + stable disease \geq 6 months) in patients receiving panitumumab rechallenge versus standard therapy (TAS-102 or regorafenib).
- 2.24 To compare the safety and tolerability of panitumumab rechallenge versus standard therapy (TAS-102 or regorafenib).
- 2.25 To compare QOL between panitumumab rechallenge versus standard therapy (TAS-102 or regorafenib) as measured by the linear analogue self-assessment (LASA) questionnaires.

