10.0 Adverse Event (AE) Reporting and Monitoring

The site principal investigator is responsible for reporting any/all adverse events to the sponsor as described within the protocol. Refer to the adverse event and serious adverse event sections of the protocol for detailed information.

NOTE: Please see Appendix V for specific AE reporting regarding the study drug panitumumab for ACCRU personnel only.

ACCRU is responsible for notifying FDA and all participating investigators in a written safety report of any of the following:

- Any suspected adverse reaction that is both serious and unexpected.
- Any findings from laboratory animal or *in vitro* testing that suggest a significant risk for human subjects, including reports of mutagenicity, teratogenicity, or carcinogenicity.
- Any findings from epidemiological studies, pooled analysis of multiple studies, or clinical studies, whether or not conducted under an IND and whether or not conducted by the sponsor, that suggest a significant risk in humans exposed to the drug.
- Any clinically important increase in the rate of a serious suspected adverse reaction over the rate stated in the protocol or Investigator's Brochure (IB).

Definitions

Adverse Event

Any untoward medical occurrence associated with the use of a drug in humans, whether or not considered drug related.

The investigator is responsible for ensuring that all adverse events observed by the investigator or reported by the subject that occur after the first dose of investigational product(s)/study treatment through the safety follow-up visit are reported using the Event CRF.

Events Meeting the Adverse Event Definition

- Any abnormal laboratory test results (hematology, clinical chemistry, or urinalysis) or other safety assessments (eg, electrocardiogram, radiological scans, vital signs measurements), including those that worsen from baseline, that are considered clinically significant in the medical and scientific judgment of the investigator (ie, not related to progression of underlying disease).
- Exacerbation of a chronic or intermittent pre-existing condition including either an increase in frequency and/or intensity of the condition.
- New conditions detected or diagnosed after study treatment administration even though it may have been present before the start of the study.
- Signs, symptoms, or the clinical sequelae of a suspected drug-drug interaction.

Definition of Serious Adverse Event

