15.18 **Drug procurement:** Each participating ACCRU treating location will fill out the pharmacy contact sheet posted in ARMS. ACCRU will send sites a site specific Drug Order Form. Sites will then send completed Drug Order Form to email address listed on the form.

Each participating ACCRU treating location will be responsible for monitoring the supply of panitumumab and will use the Drug Order Request Form to order additional supplies as needed.

Outdated or remaining drug is to be destroyed on-site as per procedures in place at each institution.

15.19a Temperature excursions that occur at the site should be reported by the site using the Temperature Excursion Form found on the ACCRU web site for this study and emailed to 'send to' address on the form.

15.19b Nursing Guidelines:

15.19b1 Patient may experience typical EGFR inhibitor related rash, which is generally acneiform in nature and may be associated with pruritis and erythema. Treat symptomatically and monitor for effectiveness.

15.19b2 Premedication is generally not required with panitumumab administrations as infusion related reactions are rare. If patients do experience a transfusion related reaction, stop the infusion, inform the MD and treat as necessary. Patient then may need premedication prior to future infusions.

15.19b3 Panitumumab must be infused via infusion pump through a 0.2 or 0.22 micron in-line filter infusion set up. Flush with 0.9% sodium chloride injection, USP before and after infusion.

15.19b4 Hypomagnesemia is seen with this agent. Monitor magnesium level prior to each infusion. If level is below normal, inform the MD.

15.19b5 Patients may experience nail related changes, including discoloration, ridging, paronychias, and/or loss of the nail itself. Instruct patients to report nail changes to the study team, as intervention may be indicated.

15.19b6 Gastrointestinal side effects including nausea, diarrhea, constipation and vomiting have been seen. Treat symptomatically and monitor for effectiveness.

15.19b7 Monitor patients closely and instruct them to report any side effects to the study team as all side effects of panitumumab in combination with chemotherapy are not known at this time.

15.19b8 Panitumumab is a protein and should be handled carefully to

avoid break down of the product. This includes both when mixing from the vial and when administering the product via IV infusion.

15.2 **Regorafenib (BAY 73-4506, Stivarga®)**

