15.27 Known potential toxicities

Consult the package insert for the most current and complete information.

Serious Adverse Effects

Hepatotoxicity: [U.S. Boxed Warning]: Severe liver toxicity and hepatic failure (sometimes resulting in death) have been observed in clinical trials; hepatocyte necrosis with lymphocyte infiltration has been demonstrated with liver biopsy. Monitor hepatic function at baseline and during treatment. Interrupt therapy for hepatotoxicity; dose reductions or discontinuation are necessary depending on the severity and persistence.

Most Common Adverse Events, >10%:

Cardiovascular: Hypertension, hemorrhage

Central nervous system: Fatigue, dysphonia, pain, fever, headache.

Dermatologic: Skin toxicity, Palmar-plantar erythrodysesthesia, rash

Endocrine & metabolic: Hypocalcemia, hypophosphatemia, hyponatremia, hypokalemia

Gastrointestinal: Appetite decreased, lipase increased, diarrhea, mucositis, weight loss, amylase increased

Hematologic: Anemia, lymphopenia, thrombocytopenia, INR increased, neutropenia

Hepatic: AST increased, ALT increased, hyperbilirubinemia

Renal: Proteinuria

Miscellaneous: Infection, pain (including gastrointestinal and abdominal pain)

Less Common Adverse Events, 1% - 10%:

Hepatic: Hepatic failure

Rare Adverse Events (Important or life-threatening), <1%:

Gastrointestinal: Gastrointestinal perforation, gastrointestinal fistula,

Cardiovascular: Cardiac ischemia or infarction

Neurologic: Reversible posterior leukoencephalopathy syndrome (RPLS)

Dermatologic: Stevens-Johnson syndrome, toxic epidermal necrolysis

Additional risks:

Hypersensitivity reactions: Hypersensitivity reactions have been reported during post-approval use of regorafenib. Because these reactions are reported voluntarily from a population of uncertain size, it is not always possible to reliably estimate their frequency or establish a causal relationship to drug exposure

Wound Healing Complications: No formal studies of the effect of regorafenib on wound healing have been conducted. Since vascular endothelial growth factor receptor (VEGFR) inhibitors such as regorafenib can impair wound healing, discontinue treatment with regorafenib at least 2 weeks prior to scheduled surgery. The decision to resume regorafenib after surgery should be based on clinical judgment of adequate wound healing. Discontinue regorafenib in patients with wound dehiscence.

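### The solicited adverse-event list names panitumumab's characteristic rash but no toxicity characteristic of regorafenib or TAS-102, and Sections 10.0 and 10.53 give different rules for collecting the low-grade events left off it

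*Combined protocol and SAP*

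**What the plan says.** **Solicited terms.** Section 10.52 states: "The following pre-treatment symptoms/conditions are to be graded at baseline and adverse events are to be graded at each evaluation using CTCAE v5.0 grading". Its table has three rows: fatigue, diarrhea and "Rash acneiform". Section 6.18 ties the required baseline grading to this list.

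**All other terms.** Section 10.53 governs CRF submission of events off the list. (It refers to events not specified in 10.5; I read this as the 10.52 list.) Item 10.531 asks for "Grade 2 AEs deemed *possibly, probably, or definitely* related to the study treatment or procedure", and item 10.532 for "Grade 3 and 4 AEs regardless of attribution to the study treatment or procedure". Deaths follow in 10.533. Grade 1 is not requested. Section 18.1 has separate forms for solicited and other adverse events.

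**A competing rule.** In its definition of an adverse event, Section 10.0 says: "The investigator is responsible for ensuring that all adverse events observed by the investigator or reported by the subject" after the first dose are reported on the Event CRF. It sets no grade or attribution limit.

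**Use of the data.** Goal 2.24 compares safety and tolerability between arms. Section 16.54 records each patient's maximum grade for each event type, reviews frequency tables for patterns, and names one between-arm test, on grade 3 or higher rates.

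**The concern.** One of the three solicited terms belongs to the experimental drug and none to either control drug. Section 15.19b1 describes the panitumumab effect: "Patient may experience typical EGFR inhibitor related rash, which is generally acneiform in nature". For regorafenib, Section 15.27 lists, above 10%, "Dermatologic: Skin toxicity, Palmar-plantar erythrodysesthesia, rash" and also hypertension, yet neither PPES nor hypertension is on the list.

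Grade 2 matters for tolerability in this trial. Section 8.2 attaches treatment actions to grade 2 PPES, symptomatic grade 2 hypertension and grade 2 oral mucositis. If 10.53 governs, whether those events reach the database depends on an attribution made with knowledge of the arm.

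Baseline grading is also affected. Section 3.25 admits patients already treated with one of the control drugs, and Section 3.28 allows residual grade 1 toxicity. Without a required baseline grade, residual PPES or mucositis cannot be cleanly separated from new toxicity.

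At stake is the low-grade part of the tolerability comparison under goal 2.24. The efficacy decision is not touched.

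**Working it through.** The plan states no figure to reproduce, so the check compares its sections, followed by a scale illustration on stated assumptions.

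**Step 1. The list against each drug's toxicity section (15.17, 15.27, 15.37).**

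| Term | Panitumumab | Regorafenib | TAS-102 | Solicited |
|---|---|---|---|---|
| Fatigue | >10% | >10% | ≥10% | yes |
| Diarrhea | >10% | >10% | ≥10% | yes |
| Acneiform rash | >10% | not listed by that name | not listed | yes |
| PPES | 1–10% | >10% | not listed | no |
| Hypertension | not listed | >10% | not listed | no |
| Mucositis/stomatitis | >10% | >10% | 1% to <10% | no |
| Nausea | >10% | in 15.295 only | ≥10% | no |
| Neutropenia | leukopenia, 1–10% | >10% | ≥10% | no, but CBC scheduled |
| Paronychia, pruritus, dry skin | >10% | not listed | not listed | no |
| Hypomagnesemia | >10% | not listed | not listed | no |

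The terms that separate a control drug from panitumumab and have no laboratory substitute are PPES and hypertension. Mucositis and nausea are common to panitumumab too.

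**Step 2. What reaches the database.**

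| | Solicited term | Off-list, 10.53 governs | Off-list, 10.0 governs |
|---|---|---|---|
| Required baseline grade | yes | no | no |
| Grade 1 | yes | no | if observed or reported |
| Grade 2 | yes | only if at least possibly related | if observed or reported |
| Grade 3–4 | yes | yes | yes |

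The filter is the same in both arms for any given term. The inequality comes from which terms are listed.

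**Step 3. Which analyses use the filtered grades.** The grade 3 or higher test (16.54) and the suspension rule on related grade 4+ events (16.4.2) do not. The maximum-grade tables do. CBC and chemistry are scheduled in both arms (Section 4.0) and have a laboratory CRF (18.1), so cytopenias can be graded from values.

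**Step 4. Scale, on assumptions only.** Let g1, g2 and g3 be the shares of a toxicity's events with maximum grade 1, 2 and 3+, and r the share of grade 2 events judged related. If 10.53 governs, the fraction of off-list events recorded is:

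- any grade: c = g3 + r × g2
- grade 2 or higher: c2 = (g3 + r × g2) / (g2 + g3)
- grade 3 or higher: 1

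The grade mixes and r are assumptions; the documents give neither.

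| g1/g2/g3 | r | c | c2 |
|---|---|---|---|
| 50/35/15% | 1.0 | 0.15 + 0.35 = 0.50 | 0.50/0.50 = 1.00 |
| 50/35/15% | 0.6 | 0.15 + 0.21 = 0.36 | 0.36/0.50 = 0.72 |
| 35/45/20% | 1.0 | 0.20 + 0.45 = 0.65 | 0.65/0.65 = 1.00 |
| 35/45/20% | 0.6 | 0.20 + 0.27 = 0.47 | 0.47/0.65 = 0.72 |

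With the same c in both arms, a recorded difference for one term is c times the true difference. A true any-grade excess of 30 percentage points would appear as 0.36 × 30 = 10.8 to 0.65 × 30 = 19.5 points. At grade 2 or higher the loss is 0% to 28%, so most of the loss is at grade 1. Acneiform rash, being solicited, has c = 1.

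**The case against.** The strongest reply is that a short solicited list is a legitimate design choice and nothing tested or decided depends on it. The only named adverse-event test uses grade 3 or higher, those events are collected whatever the attribution, and Section 16.5 treats secondary p-values as descriptive. Each term is handled identically in both arms. Panitumumab also loses low-grade events, since paronychia, pruritus, dry skin and hypomagnesemia are off the list. Grade 2 needs only possible attribution, and labelled effects such as PPES on regorafenib will probably get it. LASA scores each cycle and the dose-modification form also bear on tolerability.

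Most of this stands and sets the limits of the point. It does not remove the difference in capture between acneiform rash and PPES or hypertension, and it does not reconcile Section 10.0 with 10.53.

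A reader might infer two stronger things. One is that the any-grade and grade 2+ tables as a whole are biased against panitumumab. The documents do not support that: the filter is common to both arms, several off-list terms are panitumumab toxicities, and the direction for total burden cannot be established. The other is that a false between-arm difference would be declared. That would require comparing rash in one arm with a different toxicity in the other, which no planned analysis does. For a single term, the effect is attenuation of a real difference.

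**Conclusion.** The point holds in a limited form. If 10.53 governs, low-grade acneiform rash is fully recorded, while a low-grade control-arm excess of PPES and hypertension is attenuated in the maximum-grade tables, and one of mucositis or nausea to a lesser extent. The gap concerns mainly regorafenib: TAS-102's cytopenias are recoverable from laboratory data, and its nausea is shared with panitumumab. If Section 10.0 governs, the grade and attribution filter disappears, but the off-list terms still lack solicitation and a required baseline grade.

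The size cannot be derived from the documents. The 36% to 65% capture at any grade rests on assumed grade mixes, on 60% to 100% of grade 2 events being judged related, and on equal capture in both arms. Grade 3 or higher comparisons, the grade 4+ suspension rule and the primary analysis are unaffected. The conflict between Sections 10.0 and 10.53 needs correcting on any reading.

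**What to change.** 1. Add PPES, hypertension, oral mucositis and nausea to the Section 10.52 table, graded in both arms at baseline and at the adverse-event assessments already scheduled in Section 4.0.
2. Leave neutropenia to the laboratory CRF. Do not add hypomagnesemia: Section 4.0, footnote 5, limits on-treatment magnesium to the panitumumab arm, so it would become another term ascertained in one arm only.
3. Make Sections 10.0 and 10.53 state one collection rule, preferably all grade 2 events regardless of attribution, and correct the cross-reference in 10.53 if 10.52 is meant.
4. If grade 2 stays filtered by attribution, say in Section 16.54 that between-arm low-grade comparisons are limited to solicited terms and that other terms are compared at grade 3 or higher.

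The cost is about four more form rows per evaluation, with no added visits. Blood pressure would have to be recorded at the scheduled exams, since Section 4.0 has no row for it although Section 15.292 refers to monitoring as outlined in the protocol. Collecting all grade 2 events adds some data entry. Low-grade data not collected prospectively are hard to recover later.

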11.0 Treatment Evaluation Using RECIST Guideline

NOTE: This study uses protocol RECIST v1.1 template dated 2/16/2011. See the footnote for the table regarding measureable disease in Section 11.44, as it pertains to data collection and analysis.

Response and progression will be evaluated in this study using the new international criteria proposed by the revised Response Evaluation Criteria in Solid Tumors (RECIST) guidelines (version 1.1) [38]. Changes in the largest diameter (unidimensional measurement) of the tumor lesions and the short axis measurements in the case of lymph nodes are used in the RECIST guideline.

11.1 Schedule of Evaluations: For the purposes of this study, patients should be reevaluated every 8 weeks.

11.2 Definitions of Measurable and Non-Measurable Disease

11.21 Measurable Disease

11.211 A non-nodal lesion is considered measurable if its longest diameter can be accurately measured as ≥ 2.0 cm with chest x-ray, or as ≥ 1.0 cm with CT scan, CT component of a PET/CT, or MRI.

11.212 A superficial non-nodal lesion is measurable if its longest diameter is ≥ 1.0 cm in diameter as assessed using calipers (e.g. skin nodules) or imaging. In the case of skin lesions, documentation by color photography, including a ruler to estimate the size of the lesion, is recommended.

11.213 A malignant lymph node is considered measurable if its short axis is ≥ 1.5 cm when assessed by CT scan (CT scan slice thickness recommended to be no greater than 5 mm).

NOTE: Tumor lesions in a previously irradiated area are not considered measurable disease.

11.22 Non-Measurable Disease

11.221 All other lesions (or sites of disease) are considered non-measurable disease, including pathological nodes (those with a short axis ≥ 1.0 to < 1.5 cm). Bone lesions, leptomeningeal disease, ascites, pleural/pericardial effusions, lymphangitis cutis/pulmonis, inflammatory breast disease, and abdominal masses (not followed by CT or MRI), are considered as non-measurable as well.

Note: ‘Cystic lesions’ thought to represent cystic metastases can be considered as measurable lesions, if they meet the definition of measurability described above. However, if non-cystic lesions are present in the same patient, these are preferred for selection as target lesions. In addition, lymph nodes that have a short axis < 1.0 cm are considered non-pathological (i.e., normal) and should not be recorded or followed.

11.3 Guidelines for Evaluation of Measurable Disease

11.31 Measurement Methods:

- All measurements should be recorded in metric notation (i.e., decimal fractions of centimeters) using a ruler or calipers.
- The same method of assessment and the same technique must be used to characterize each identified and reported lesion at baseline and during follow-up. For patients having only lesions measuring at least 1 cm to

less than 2 cm must use CT imaging for both pre- and post-treatment tumor assessments.

- Imaging-based evaluation is preferred to evaluation by clinical examination when both methods have been used at the same evaluation to assess the antitumor effect of a treatment.

11.32 Acceptable Modalities for Measurable Disease:

- Conventional CT and MRI: This guideline has defined measurability of lesions on CT scan based on the assumption that CT slice thickness is 5 mm or less. If CT scans have slice thickness greater than 5 mm, the minimum size for a measurable lesion should be twice the slice thickness.
- As with CT, if an MRI is performed, the technical specifications of the scanning sequences used should be optimized for the evaluation of the type and site of disease. The lesions should be measured on the same pulse sequence. Ideally, the same type of scanner should be used and the image acquisition protocol should be followed as closely as possible to prior scans. Body scans should be performed with breath-hold scanning techniques, if possible.
- PET-CT: If the site can document that the CT performed as part of a PET-CT is of identical diagnostic quality to a diagnostic CT (with IV and oral contrast), then the CT portion of the PET-CT can be used for RECIST measurements and can be used interchangeably with conventional CT in accurately measuring cancer lesions over time.

11.33 Measurement at Follow-up Evaluation:

- In the case of stable disease (SD), follow-up measurements must have met the SD criteria at least once after study entry at a minimum interval of 8 weeks (see Section 11.44).
- The cytological confirmation of the neoplastic origin of any effusion that appears or worsens during treatment when the measurable tumor has met criteria for response or stable disease is mandatory to differentiate between response or stable disease (an effusion may be a side effect of the treatment) and progressive disease.
- Cytologic and histologic techniques can be used to differentiate between PR and CR in rare cases (e.g., residual lesions in tumor types such as germ cell tumors, where known residual benign tumors can remain.)

